6.2 Secondary outcomes

Maternal-

- Feasibility of CGM use for GDM screening
- Diabetic medication: use of any glycemic control agent during pregnancy
 or 6- week postpartum period.
- Polyhydramnios during pregnancy not related to known fetal anomaly
- Ultrasound diagnosis of estimated fetal weight >90%ile in the third trimester based on the (using the nomogram published by Duryea EL et al) (19)
- Preterm birth: delivery less than 37 weeks of gestation

- Induction of labor
- Pregnancy-induced hypertension: gestational hypertension, preeclampsia with or without severe features, HELLP syndrome, or eclampsia per ACOG guidelines.
 - Gestational hypertension: new-onset hypertension (systolic ≥ 140
 mm Hg or diastolic ≥ 90 mm Hg) without proteinuria
 - Preeclampsia: hypertension (systolic ≥ 140 mm Hg or diastolic ≥ 90 mm Hg) with proteinuria or serum laboratory abnormalities
 (platelets ≤ 100,000, serum aspartate aminotransferase ≥ 80 IU/mL, creatinine ≥ 1.2 mg/dL. They are classified as with or without severe features.
 - Severe features: systolic ≥ 160 mm Hg, diastolic ≥ 110 mm
 Hg, persistent headache, pulmonary edema, or any serum
 laboratory abnormalities as above
 - Proteinuria: protein excretion exceeding 300mg in 24 hours,
 a protein: creatinine ratio of ≥ 0.3 or 1+ proteinuria or greater
 on urine dipstick
 - HELLP Syndrome: hemolysis (serum bilirubin ≥ 1.2, low serum haptoglobin ≤ 25, lactate dehydrogenase (LDH) > 2 times upper limit of normal based on laboratory-specific reference ranges or severe anemia unrelated to blood loss), elevated liver enzymes (aspartate aminotransferase (AST) or alanine aminotransferase (ALT) > 2 times the upper limit

of normal based on laboratory-specific reference ranges) and low platelet count (≤ 100,000)

- o Eclampsia: seizures
- Admission for poor glucose control
- Primary cesarean section
- Postpartum hemorrhage: defined as ≥ 1000ml or need for blood transfusion
- Endometritis
- Wound complications
- Diagnosis of type 2 diabetes during postpartum (according to the 1h 75g
 GTT)

Neonatal:

- Large for gestational age (LGA): weight over 90th percentile of the expected value according to gestational age (using the nomogram by Duryea EL et al). (19)
- Shoulder dystocia: defined as the need for any extra maneuvers, other than gentle downward traction of the fetal head to deliver the fetal body after the fetal head has been delivered
- o Birth injury: skull, clavicular, humerus fracture, or brachial plexus injury
- Neonatal hypoglycemia defined as requiring intravenous or oral glucose
- Respiratory distress: the need for at least 4 hours of respiratory support with supplemental oxygen, continuous positive airway pressure, or ventilation at the first 24 hours of life

#UTHealth

- Fetal or neonatal death (within 28 days of birth)
- Apgar score < 7 at 5 min
- Neonatal intensive care unit (NICU) admission
- NICU length of stay
- Neonatal hypoglycemia: ≤40 mg/dL in the first 24 hours of life and less than 50 mg/dL after or requiring medical therapy
- Neonatal polycythemia defined as hematocrit (Hct) or hemoglobin (Hgb)
 level above the upper limit of normal (>2 standard deviations) for
 gestational and postnatal age.
- Neonatal hyperbilirubinemia requiring phototherapy
- Maximum bilirubin level
- Umbilical cord pH (arterial and venous)
- Need for intravenous glucose therapy
- Small for gestational age, defined as a weight below 10th percentile of the expected value according to gestational age (using the nomogram published by Duryea EL et al) (19)

Mother-Infant Dyad

- Total health system costs for mothers and infants
- Cost-effectiveness of CGM relative to usual care, assessed as the total
 incremental maternal and neonatal health system costs (savings) per
 prevented mother-infant dyad from developing a maternal adverse outcome
 (preterm birth, induction of labor, pregnancy-induced hypertension, admission
 for poor glucose control, primary cesarean section, postpartum hemorrhage,

#UTHealth

IRB NUMBER: HSC-MS-22-0153

endometritis or wound complications) or a neonatal adverse outcome (LGA, shoulder dystocia, birth injury, neonatal hypoglycemia, respiratory distress, fetal or neonatal death within 28 days of birth).

Costs will be assessed from the health system perspective based on the total costs for all the services provided to both the participating women and their neonates from randomization through either 6-weeks postpartum or discharge home (whichever is later). Hospital costs incurred within the Memorial Hermann Hospital System (MHHS) will be obtained from claims data and will be based on hospital-specific costs as assigned in the cost-accounting system for each of the 14 hospitals of the MHHS. Hospital costs incurred at hospitals outside of MHHS will be estimated based on mean costs of these encounters at MHHS. Costs for inpatient and outpatient services provided by the UTH physicians will be estimated based on UTH claims data and Relative Value Units (RVUs) from the Medicare Fee Schedule. The costs for the intervention group will be augmented by the acquisition costs of the Dexcom G6 Pro device, which will be based on the average wholesale price as listed in the Micromedex Redbook. All costs will be inflated to the year of analysis based on the Consumer Price Index for medical services.

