3. HYPOTHESIS AND OBJECTIVE

3.1 Hypothesis:

We hypothesize that compared to usual care with the two- step screening method, CGM will increase detection of GDM and reduce maternal and neonatal adverse outcomes and health system costs related to GDM. CGM will also be shown to be highly cost-effective in preventing mother-infant dyads from developing maternal or neonatal adverse outcomes. Cost effectiveness may be achieved be either reducing maternal or neonatal health system costs without increasing the rate or heath system costs of adverse maternal or neonatal outcomes. By highly cost effective, we mean that CGM will lie within the dominant quadrant – i.e. the lower right quadrant – of the cost-effectiveness plane (Figure 1).

Figure 1. Cost Effectiveness Plane

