- Group 2 will have the device in place for a total of 7 days and reviewed by the Diabetes team after 7-10 days after CGM placement. The recommended range for glucose during pregnancy is defined as 63-140 mg/dL (18). The time above range has been defined as ≥ 140 mg/dL, greater than 10% of total CGM

placement time. Based on the results of our prospective observational study of blinded CGM placement at time of one-hour GCT of pregnant people \leq 30 weeks a CGM metric of time above range \geq 10% was associated with higher rates of adverse neonatal outcomes.

- The following criteria will currently be used to diagnose gestational diabetes in the CGM group:
 - Time above range (≥140 mg/dL) ≥ 10% of the time while using CGM or
 - Average glucose≥130 mg/dL or
 - Any glucose value ≥200 mg/dL
- Group I will receive routine prenatal care follow-up depending upon one-hour glucose results as written above.
- Group 2 will complete CGM and proceed with treatment if positive screening is found, as written above.
- Management of GDM for both groups would include:
 - Consultation and follow up with Certified Diabetes Care and Education
 Specialist (CDCES)
 - The patients will be instructed to self-monitoring of blood glucose (SMBG)
 levels four times a day through a glucometer: fasting, 1-2 hour
 postprandial as recommended by the ACOG guidelines.
 - Patients will be managed according to the ACOG recommendations of goals (2):
 - Fasting: ≤ 95 mg/dL
 - 1 hour postprandial: ≤ 140 mg/dL

- 2 hour postprandial: ≤ 120 mg/dL
- Initiation of medication if consistently elevated blood sugars following diet adjustment per provider discretion
- Participants will be asked to continue to follow up as the standard of care.
- No extra visits will be scheduled
- Both groups will be followed throughout pregnancy, delivery, and postpartum.
- A release of records form will be signed at randomization so that in case the participant delivers at another center; we can still obtain records from the delivery.
- The research team will collect participant data, including demographic characteristics, medical history, obstetric history, labor course, and maternal and neonatal outcomes, by reviewing the electronic medical records and surveying the people during prenatal visits and the 6- week postpartum clinical appointment.
- All participants will receive a \$20 gift card after completing the diabetes screening (i.e., 1hGCT/3h OGTT if screened positive/7 days with GCM).

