7.2 Statistical and analysis plan

An intention to treat analysis will be conducted. All outcomes will be analyzed using generalized linear models (GLMs) and will include stratifying variables of BMI and clinic site as covariates. Primary outcome and all other binary outcomes will be analyzed with a logistic model. Secondary outcomes will be analyzed using appropriate distributional assumptions, i.e. negative binomial for counts and normal for continuous outcomes. We will report relative risks or group mean differences and 95% confidence intervals (CIs). Differences in costs will be assessed using a generalized linear model (GLM) with log-

link and gamma distribution. We will also compute the incremental cost-effectiveness ratio (ICER) of the total health system costs (savings) per prevented mother-infant dyad from developing an adverse outcome using a joint GLM with log link for costs and probit for maternal or neonatal adverse outcomes. We will induce dependency between costs and the adverse outcomes through shared random effects in the joint model.

Planned Bayesian analysis:

We will also conduct a Bayesian analysis of the primary outcome and of costs and cost-effectiveness. Sample size calculations using a Bayesian analysis with different probability thresholds are presented in Table 4. The composite primary outcome will be evaluated with a Bayesian binomial model. Finally, we conservatively set a neutral prior probability centered at a relative risk (RR) of 1.0 (*i.e.*, a priori no effect on the outcome) and a 95% credible interval of 0.3-3.3 encompassing the largest likely effect size for major outcomes in randomized trials. This neutral prior will also be used to assess cost differences between the two treatment groups. Finally, we will report RR and 95% credible intervals and the probability of reduced adverse neonatal outcomes and costs, as well as the probability that the ICER will fall in the dominant quadrant of the cost-effectiveness plane (Figure 1).

Table 4: Bayesian power to declare efficacy depending on level of evidence (probability threshold)

Control Rate	Treatment Rate	# patients /group	Prob(RR<1) > specified threshold					
			70%	75%	80%	85%	90%	95%
0.4	0.24	60	0.92	0.89	0.85	0.79	0.71	

	0.75	0.82	0.85	0.89	0.93	120	0.28	0.4
	0.90	0.93	0.96	0.98	0.98	110	0.24	0.4
	0.90	0.94	0.96	0.97	0.98	210	0.28	0.4
0.80	0.89	0.93	0.95	0.97	0.98	236	0.245	0.35
0.80	0.89	0.93	0.95	0.97	0.98	294	0.21	0.30

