10. DATA HANDLING AND RECORD-KEEPING

10.1 Access to source documents

Research personnel will perform data collection through the abstraction of participant electronic medical records from multiple sites. Demographics, variables, and outcomes will be collected and entered into a Redcap database and the Dexcom data capture platform. Attached to this protocol is a detailed list of variables that will be collected. Data will be obtained from randomization up until 6 weeks postpartum.

10.2 Records Retention:

Data will be collected and de-identified in the UTHealth Redcap system. At the time of study completion, approved protocol and all other supporting documents pertaining to the project will be retained. Data will be de-identified and available for future analysis. Following completion of the study and analysis of data, the de-identified data will be shared to Dexcom Inc.

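### Postpartum type 2 diabetes is compared between arms by relative risk, but no postpartum glucose test is scheduled for all participants and the plan does not say how untested women are counted

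*Combined protocol and SAP*

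**What the plan says.** Section 6.2 includes among the maternal secondary outcomes "Diagnosis of type 2 diabetes during postpartum (according to the 1h 75g" GTT). It gives no glucose cut-off, test date or denominator.

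On follow-up, section 5.4 says "Participants will be asked to continue to follow up as the standard of care" and "No extra visits will be scheduled". Outcome data come from the medical record and from "surveying the people during prenatal visits and the 6- week postpartum clinical appointment"; no glucose test is mentioned at that appointment. Section 10.1 closes the window: "Data will be obtained from randomization up until 6 weeks postpartum".

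On the difference expected between arms, section 3.1 hypothesises that "CGM will increase detection of GDM". Section 5.1 states that physicians and patients cannot be blinded.

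On analysis, section 7.2 says "An intention to treat analysis will be conducted. All outcomes will be analyzed using generalized linear models (GLMs") and "Primary outcome and all other binary outcomes will be analyzed with a logistic model", with relative risks and 95% confidence intervals reported. It has no rule for participants without a postpartum result.

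On the test itself, Table 1 in section 1 heads every 75 g test as a 2-hour test and uses the 1-hour heading for the 50 g challenge.

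**The concern.** An outcome defined by a test result exists only where the test is done. Here the protocol leaves testing to routine care. The GDM diagnosis, the obvious trigger for testing after delivery, is made after randomisation by the method under study. If testing depends on that diagnosis and the arms differ in how often it is made, the arms differ in their chance of having postpartum diabetes found, even when its true frequency is the same.

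The analysis rule does not protect against this. Counting untested women as negative compares detection as well as disease. Restricting to tested women compares two groups selected after randomisation, which may differ in underlying risk. Either way, a testing artefact could be published as a harm or a benefit of CGM screening.

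**Working it through.** **Plan's own figures.** None is given for this outcome. Section 7.1 gives 734 and 10% loss: 734 / 0.90 = 815.6, rounded up to 816, so 816 / 2 = 408 per arm. Section 7.1 describes the 734 as needing a GDM diagnosis. I read it as the number analysed, because the next step inflates it to the number enrolled.

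**Inputs**
- Enrolled: 408 per arm (from section 7.1).
- Labelled GDM in the control arm: 10% (the background US figure in section 1; the protocol gives no rate by arm).
- Labelled GDM in the CGM arm: 15-20% (assumption).
- Testing: all labelled women and no others (assumption).
- Positivity in two-step-labelled women: 5% (assumption).
- The CGM-labelled group contains women with the same risk as the two-step-labelled 10%, plus extra women with positivity q, varied from 0% to 5% (assumption).
- No true effect of arm.

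**Formulas**, with d = extra proportion labelled (0.05 or 0.10):
- Untested counted as negative: RR = (0.10 × 0.05 + d × q) / (0.10 × 0.05).
- Tested women only: RR = [(0.10 × 0.05 + d × q) / (0.10 + d)] / 0.05.

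**Numbers tested.** Control 408 × 0.10 = 41; CGM 408 × 0.15 = 61 or 408 × 0.20 = 82. Control cases: 408 × 0.10 × 0.05 = 2.0.

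| CGM labelled | q | Cases, control vs CGM | RR, untested = negative | RR, tested only |
|---|---|---|---|---|
| 15% | 5% | 2.0 vs 3.1 | 1.5 | 1.00 |
| 15% | 2% | 2.0 vs 2.4 | 1.2 | 0.80 |
| 15% | 0% | 2.0 vs 2.0 | 1.0 | 0.67 |
| 20% | 5% | 2.0 vs 4.1 | 2.0 | 1.00 |
| 20% | 2% | 2.0 vs 2.9 | 1.4 | 0.70 |
| 20% | 0% | 2.0 vs 2.0 | 1.0 | 0.50 |

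At q = 2% the same data point to apparent harm under one rule and apparent benefit under the other.

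**Does testing cause this?** Write the observed rate as p × [s × tL + (1 − s) × tU], where p is true prevalence (equal in both arms), s the share of true cases labelled, and tL and tU the testing probabilities in labelled and unlabelled women. If tL = tU = t, the rate is p × t in both arms and RR = 1.00 whatever the labelling. If tU = 0, RR is the ratio of the shares: 0.80 / 0.60 = 1.33, or 0.90 / 0.50 = 1.80. Since the CGM share cannot exceed 1, an RR of 2.0 requires two-step screening to label no more than half of the true cases.

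**Precision.** For 4 versus 2 cases in 408 per arm, the standard error of log RR is √(1/4 + 1/2 − 2/408) = 0.863, so the 95% interval is 2.0 × exp(±1.96 × 0.863) = 0.37 to 10.9.

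**Test label.** Section 6.2 pairs a 1-hour label with a 75 g load. In Table 1, tests headed 1h use 50 g and tests headed 2h use 75 g. No cut-off for postpartum type 2 diabetes is given in the document.

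**The case against.** The strongest reply is that the bias is conditional. It needs testing driven by the label and more labelling in the CGM arm; an excess under the untested-as-negative rule also needs true cases among the extra labelled women. The document does not say who is tested postpartum and gives no labelling or testing rates. This stands. A reader might infer that the CGM arm is certain to be tested more and to show more diabetes; the text supports a likely risk, not a certainty, and a true treatment effect could offset it.

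A reader might also infer that section 7.2 treats untested women as free of diabetes. It does not say so; they could equally be excluded as missing. Nor does the apparent relative risk equal the ratio of labelling rates in general: that holds only if the extra CGM-labelled women are as often positive as the two-step-labelled women.

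A reader might call the test label a direct conflict with Table 1. That is too strong: the table covers GDM screening in pregnancy, and two of its 75 g entries (American Diabetes Association one-step and the international study group) carry a 1-hour threshold. What stands is a label that does not match the headings and has no cut-off. The variable list that section 10.1 describes as attached was not available and might define the outcome.

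Finally, it can be argued that stating who is tested and how untested women are handled would be enough, without giving up the comparison. That would cure the silence but not the contrast: with label-driven testing, neither handling rule yields an interpretable randomised comparison.

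**Conclusion.** The point holds in this form: a test-defined outcome, with no postpartum test scheduled for all, is subject to a between-arm relative risk with no rule for untested women, while the protocol itself expects the arms to differ in GDM diagnoses. Under the stated assumptions and no true effect, the apparent relative risk is 1.0-2.0 if untested women are counted as negative, with 2.0 as the upper end, and 0.5-1.0 if only tested women are analysed. The 10%, 15-20% and 5% inputs and label-only testing are assumptions for illustration, not trial rates. With about 2 versus 2-4 expected cases, any estimate would also be very imprecise.

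Reach is limited. The outcome is secondary and belongs neither to the primary composite in section 6.1 nor to the maternal list in the cost-effectiveness outcome. The undefined test label is a separate, smaller defect that stands whether or not testing is unequal.

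**What to change.** In section 6.2, mark postpartum type 2 diabetes as descriptive and report three counts by arm: diagnosed with GDM, tested postpartum, and positive among those tested. In section 7.2, exempt the item from the logistic model and from the relative risk. Reconcile the test named in section 6.2 with the test headings in Table 1, and state one test and one criterion by which results are classified; which test is right is for the investigators to settle.

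The cost is a wording change in two sections, with no new test, visit or participant. The downside is that one secondary contrast, with very few expected events, becomes descriptive.

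### Section 6.2 promises total health system costs but names no source or price for outpatient GDM drugs and self-monitoring supplies, and leaves CDCES visits and the glucose tests to chance billing

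*Combined protocol and SAP*

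**What the plan says.** Section 6.2 (Mother-Infant Dyad) gives a wide scope: "Costs will be assessed from the health system perspective based on the total costs for all the services provided to both the participating women", with the infants included as well. The window runs from randomization to six weeks postpartum or discharge, whichever comes later. The sources that follow are narrower:

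- MHHS hospitals: "Hospital costs incurred within the Memorial Hermann Hospital System (MHHS) will be obtained from claims data", valued from each hospital's cost-accounting system.
- Other hospitals: imputed from MHHS mean costs.
- Professional services: "Costs for inpatient and outpatient services provided by the UTH physicians will be estimated based on UTH claims data" and Medicare RVUs.
- Device: "The costs for the intervention group will be augmented by the acquisition costs of the Dexcom G6 Pro device", at the Redbook average wholesale price.

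Section 5.4 sets out what a GDM diagnosis leads to in either arm: CDCES consultation and follow-up, self-monitoring at "levels four times a day through a glucometer", and "Initiation of medication if consistently elevated blood sugars following diet adjustment per provider discretion". It also gives every Group 1 participant the 50 g test, with a 100 g test after a positive result. Section 3.1 hypothesises that "CGM will increase detection of GDM and reduce maternal and neonatal adverse outcomes".

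Reduced health system cost is one of the two primary objectives in section 3.2. Section 7.2 reports the probability of reduced cost and the probability that the ICER falls in the dominant quadrant. It adds no cost component and no sensitivity analysis on cost scope.

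**The concern.** The scope and the sources do not match. An analyst working only from the named sources could not cost a meter, a test strip or a drug dispensed to an outpatient. Only diagnosed participants use these items, so the gap differs between arms if the arms differ in diagnoses, and the trial's hypothesis is that they will. On that component the CGM arm would be under-costed.

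CDCES visits and the glucose tests are in a different position. They are not named, but they may reach the data through UTH or MHHS claims, and the plan does not say whether they do.

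Two reported quantities are at stake: the probability of lower cost and the probability of dominance. Both depend on the sign of the cost difference. The device manufacturer funds the remainder of the study (section 11), so a complete and explicit list of cost items also helps the result's credibility.

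**Working it through.** The plan states no cost, cost SD, unit price or detection rate, so there is no figure to reproduce. The check has two parts.

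**Resources set against sources**

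- Admissions, deliveries, neonatal stays and drugs given in hospital: covered by hospital costs, inside or outside MHHS.
- UTH physician visits: covered by UTH claims and RVUs.
- CGM device: covered at Redbook price, intervention group.
- CDCES visits: covered only if billed through UTH or MHHS.
- 50 g and 100 g tests: covered only if billed through UTH or MHHS.
- Meters, strips and outpatient glucose-lowering drugs: no source, quantity or price. Section 6.2 records use of any glycemic agent as an outcome but attaches no cost.

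**Size of the drug and supply gap**

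From the documents: entry at 24 to 30 weeks, CGM review 7 to 10 days after placement, four tests a day, 816 enrolled (408 per arm).

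Assumed: delivery at 39 weeks; USD 0.20 to 1.00 per test; USD 0 to 500 of outpatient drugs per diagnosed participant on average; 5 to 20 percentage points more diagnoses with CGM; cost SD of USD 5,000 to 15,000.

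1. Tests per diagnosed participant = days from diagnosis to delivery × 4.
   - Latest diagnosis, 30 weeks plus 10 days: 53 days × 4 = 212.
   - Earliest, 24 weeks plus 7 days: 98 days × 4 = 392.
2. Uncounted cost per diagnosed participant = tests × price + drugs.
   - Low: 212 × 0.20 + 0 = USD 42.
   - Middle: 300 × 0.50 + 100 = USD 250.
   - High: 392 × 1.00 + 500 = USD 892.
3. Understatement per randomised participant = extra detection × that cost.
   - Low: 0.05 × 42.4 = USD 2.
   - Middle: 0.10 × 250 = USD 25.
   - High: 0.20 × 892 = USD 178.
4. Standard error of the cost difference = SD × √(2/408) = 0.070 × SD, which is USD 350 to 1,050.
5. Shift in the probability of lower cost, when the true difference is zero, = Φ(gap/SE) − 0.5.
   - USD 25: Φ(0.071) − 0.5 = 0.03 and Φ(0.024) − 0.5 = 0.01.
   - USD 178: Φ(0.51) − 0.5 = 0.19 and Φ(0.17) − 0.5 = 0.07.

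   In each pair the first value uses the smaller SD. Zero difference is where the shift is greatest.

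**The opposing item**

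The 50 g test applies to all of Group 1, so its cost is not diluted by a detection difference. If glucose testing fell outside the claims data, an average of USD 25 per control participant would cancel the middle case exactly.

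**The case against.** The scope sentence covers all services and excludes nothing. Section 10.1 refers to an attached variable list that is not in the text available, so one cannot show that drug or supply data will go uncollected. This stands: the supportable statement is that the plan names no source or price, not that it has decided to leave the items out.

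A health system perspective may legitimately omit items that payers or patients buy outside the system. The device can be treated differently because it is the intervention itself and is applied in the clinic. This stands in part. It would be a recognised scope choice, but the plan does not say it has made it, and its stated scope points to a full total.

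A reader might infer that the downstream cost of a more sensitive screen is missing, or that the whole cost comparison leans toward CGM. The documents support neither. Hospital care and UTH visits after diagnosis are counted. The control arm's glucose tests are no better specified than the treatment items and could push the other way. The lean on drugs and supplies itself depends on CGM diagnosing more GDM, a hypothesis for which the plan gives no size.

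Section 7.2 also sets no decision threshold for the cost probability, so no stated rule can be shown to flip. Costs are a secondary outcome, and the neonatal composite is unaffected.

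**Conclusion.** The gap is real but limited. The named sources do not deliver the stated total: outpatient glucose-lowering drugs and self-monitoring supplies have neither quantity nor price, and CDCES visits and glucose tests are covered only if they happen to be billed through UTH or MHHS. If CGM raises detection, the first omission favours CGM on that component. The net direction over all unspecified items is uncertain.

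The drug and supply gap is about USD 2 to 178 per randomised participant, with a middle case of USD 25. Against the assumed standard error that is at most about half a standard error (178/350) and usually far less. These figures rest wholly on assumed prices, drug spending, extra detection, delivery time and cost SD. The gap could alter the reading of the cost result only when the cost difference is near zero. It is still worth closing, because cost reduction is a stated primary objective and the remedy is cheap.

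**What to change.** In section 6.2, for both arms:

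- Cost self-monitoring supplies from GDM diagnosis to delivery, using the testing frequency already in section 5.4, at the Redbook price source already used for the device.
- Cost outpatient glucose-lowering drugs at the same price source.
- Cost CDCES visits and the 50 g and 100 g tests from UTH or MHHS records, or from the Medicare fee schedule where they are not billed there.

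In section 7.2, report the cost difference, the ICER and the dominance probability with and without the drug and supply items. If the sponsor intends a narrower perspective that leaves some items out, section 6.2 should say so, and the version with them becomes the sensitivity analysis. Settle this before cost data are analysed.

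The cost is a few sentences, a short unit-price table and modest extra abstraction. Use of a glycemic agent is already an outcome, but the visible text does not show that the agent and its start and stop dates are collected, so those fields may have to be added. The cost result may also be slightly less favourable to CGM.
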